3.0 OBJECTIVES

3.1 Study Objectives

3.1.1 Primary Objectives

- 1) To estimate the efficacy of repeated doses of LACTIN-V (2×10^9 cfu/dose) as compared to placebo in preventing BV recurrence by 12 weeks following treatment of BV with MetroGel
- 2) To assess the safety of LACTIN-V over 24 weeks by comparing the incidence of AEs between individuals randomized to LACTIN-V or placebo

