3.2.2 Primary Safety Outcome Measure

The proportion of participants reporting product-related AEs and SAEs in each study arm through Visit 7 (Week 24, Day 168)

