11.3 Study Hypotheses

There are two planned formal tests of hypotheses which compare LACTIN-V to placebo, with respect to the primary safety and efficacy outcome measures. The first hypothesis test compares the proportion of participants in each study arm who experience AEs or SAEs considered product related following the first dose of study product through Visit 7 (Week 24, Day 168). The second hypothesis test compares the proportion of participants in each study arm who experience BV recurrence by Visit 4 (Week 12, Day 84).

The null hypothesis for each comparison is that there is no difference in proportions between study arms, with a two-sided alternative. The test for the primary safety hypothesis will be conducted using the Fisher's exact test at the 5% two-sided level of significance without adjustment for multiplicity. The test for the primary efficacy hypothesis will be conducted using the Pearson's chi-square test at the 5% two-sided level of significance without adjustment for multiplicity. No adjustments for multiplicity will be used as this is a Phase II-b trial which will provide screening evidence about safety and efficacy for a subsequent Phase III trial.

The primary safety hypothesis will be tested in the safety data analysis population. The primary efficacy analysis will be conducted in the Complete Case analysis population, and repeated as a secondary analysis in the modified intent-to-treat and Per Protocol analysis populations. See Section 11.6.2 for definitions of and rationales for use of the analysis populations.

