11.6.3 Safety Analyses

Solicited AEs will be analyzed by taking the most severe response over the follow-up period, dichotomizing into a binary variable (none versus mild, moderate, or severe) and using standard techniques, such as exact confidence intervals, to summarize the event rates.

Standard summary statistics, including 95% confidence intervals will be computed. Additionally, graded results may either be analyzed as a binary variable (normal, abnormal) or multinomial variable (Grade 0, Grade 1, Grade 2, Grade 3) using either logistic regression or ordinal logistic regression respectively to make treatment group comparisons.

Unsolicited AEs will be coded by MedDRA® for preferred term and system organ class. The proportion of participants and exact 95% confidence intervals of AEs in aggregate, as well as by MedDRA® categories, will be computed. The number of SAEs will be reported by a detailed listing showing the type, MedDRA® coding, relevant dates (treatment dosing dates and AE onset and resolution dates), severity, relatedness, and outcome for each event.

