11.6.3.1 Analysis of Primary Safety Outcome Measure

The primary safety outcome measure is the proportion of participants reporting product-related AEs and SAEs in each study arm through Visit 7 (Week 24, Day 168).

The outcome will be assessed in the safety analysis population. The outcome will be reported by study arm. The point estimates for the arm-specific proportions and difference in proportions along with the corresponding standard errors will be reported. Fisher's exact test at the 5% two-sided level of significance level without adjustment for multiplicity will be used for the comparison of proportions between study arms.

As described in Section 11.6.3, additional descriptive analyses of adverse event data and clinical safety laboratory values will be performed.

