6. GENERAL STATISTICAL CONSIDERATIONS

6.1. General Principles

Tabulations will be used extensively to summarize the data. All continuous variables will be summarized using the following descriptive statistics: n (sample size), mean, standard deviation, median, maximum, and minimum. The frequency and percentages (based on the sample size) of observed levels will be reported for all categorical measures. Wilson confidence intervals for binomial proportions and differences in binomial proportions will be computed for efficacy variables. Blaker confidence intervals for binomial proportions and differences in binomial proportions will be computed for safety variables. For the hypothesis tests comparing treatment groups with respect to safety outcomes, the two-sided Fisher's Exact test will be used. For the hypothesis tests comparing treatment groups with respect to efficacy outcomes, the two-sided Chi-Square test will be used. For all tests, a 5% two-sided significance level will be used.

For all efficacy outcome measures, the Complete Case population (see Section 6.3) will be used as the primary analysis population and the Per Protocol, modified Intent-to-Treat, and Intent-to-Treat populations will be used as secondary analysis populations. For all safety analyses, the Safety population will be used as the analysis population.

All summary tables will be structured with a column/sub-table for each treatment group (LACTIN-V, Placebo, and All Subjects). In general, all data will be listed by treatment group and/or subject, and when appropriate by visit number within subject. The total population size relevant to that table/column if applicable, including any missing observations will be displayed in the tables.

Note that in the data listings, Subject ID is the unique subject identifier, not the Study ID used on study and dates will not be included, only Study Day. Study Day 1 will be the day of the first dose of treatment.

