9.3.1. Solicited Events and Symptoms

Solicited local and systemic events will be captured on a memory aid starting on Day 1, the first day of therapy continuing through Visit 7 (Week 24, Day 168) and graded on a scale of 0 (absent), 1 (mild), 2 (moderate) and 3 (severe). Solicited local events include vaginal bleeding other than menstruation, abnormal vaginal discharge, abnormal vaginal odor, genital itching, genital burning, external genital irritation, external genital swelling, and genital rash. Solicited systemic events include nausea, vomiting, abdominal pain/cramps, diarrhea, constipation, pain/burning with urination, frequent urination, blood in urine, and headache.

Any symptom that is present at the time that the subject is screened or enrolled should be considered as baseline and not reported as a solicited AE. However, if it deteriorates at any time during the study, it will be recorded as a solicited AE. If a symptom is reported that was not present at baseline, it will also be recorded as a solicited AE. Treatment-emergent solicited adverse events will be identified by comparing the severity of the baseline solicited symptoms with the severity of the post-baseline solicited symptoms. If the severity increases post-baseline or the symptoms appear post-baseline when it was 'None' at baseline, then the symptom will be considered to be treatment-emergent.

The number and percent of subjects reporting at least one treatment-emergent solicited adverse event will be summarized for each solicited adverse event and any solicited adverse event along with the 95% Blaker CI and presented in [Table 108](#). Section 6.1 provides pseudo SAS code to use for calculating confidence intervals.

For each treatment-emergent solicited adverse event, the maximum severity over 24 weeks after the first dose will be summarized for the Safety population. The number and percentage of subjects reporting each solicited adverse event will be summarized by the maximum severity and actual treatment group along with the 95% Blaker CIs. For each event, the denominator is the number of subjects with non-missing data for the solicited adverse event being summarized. See [Table 109](#), [Table 110](#), [Table 111](#), and [Table 112](#) and [Figure 41](#) and [Figure 42](#).

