9.3.2. Unsolicited Adverse Events

The primary safety endpoint is the proportion of subjects reporting product-related AEs and SAEs in each study arm following the first dose of study product through Visit 7 (Week 24, Day 168). The number of subjects, the proportion of subjects who experienced unsolicited AEs and SAEs following the first dose of the study product through Visit 7 (Week 24, Day 168), and the 95% Blaker CIs for the proportion of subjects who experienced unsolicited AEs and SAEs related to study product through Visit 7 will be presented for the safety population and actual treatment group. In addition, the difference in proportions between the LACTIN-V arm and the Placebo arm and 95% Blaker CIs will be presented in [Table 125](#). The proportion of subjects in each treatment group who experience product-related AEs following the first dose of the study product through Visit 7 (Week 24 Day 168) will be tested using a Fisher's exact test at the 5% two-sided level of significance level without adjustment for multiplicity in the safety analysis population. See Section 6.1 for pseudocode for calculating p-values and CIs.

The proportion of subjects reporting at least one unsolicited adverse event will be summarized by MedDRA system organ class and preferred term for all subjects and each actual treatment group. Denominators for percentages are the number of subjects who received the study product being summarized. A 95% Blaker CI will be presented for each MedDRA system organ class and preferred term (Table 126). Adverse events by subject will be presented in Listing 20.

The following summaries for unsolicited adverse events will be presented by MedDRA system organ class, preferred term, and treatment group:

- Incidence and percentage of subjects by maximum severity and maximum relationship to study product, including Frequency (Event level) of events for all subjects and by actual treatment received (Table 127 and Table 128);
- The number of adverse events occurring in 5% of subjects in any treatment group will be presented by MedDRA system organ class, preferred term, and treatment group in Table 129;
- The number of subjects reporting adverse events occurring in 5% of subjects in any treatment group will be presented by MedDRA system organ class, preferred term and treatment group in Table 130;
- Subject listing of non-serious adverse events of moderate or greater severity (Table 131);

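### The safety objective compares AE incidence between arms, but the SAP estimates a between-arm difference only for product-related unsolicited AEs; solicited events and all-cause AEs get none

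*Protocol*

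**What the plan says.** **Objective.** Protocol 3.1.1 states the second primary objective as: "To assess the safety of LACTIN-V over 24 weeks by comparing the incidence of AEs between individuals randomized to LACTIN-V or placebo". It is not restricted to related events. SAP 3.1.1 repeats it.

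**Primary safety outcome and test.** Protocol 3.2.2 narrows the outcome: "The proportion of participants reporting product-related AEs and SAEs in each study arm through Visit 7". Protocol 11.3 says "There are two planned formal tests of hypotheses which compare LACTIN-V to placebo". One is the primary efficacy test and the other is Fisher's exact test on product-related AEs and SAEs.

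**Further safety analyses in the protocol.** Section 11.6.3 asks for solicited events to be dichotomised and summarised with exact intervals, and for unsolicited AEs to be given as proportions with exact 95% intervals. It adds that graded results *may* be modelled "using either logistic regression or ordinal logistic regression respectively to make treatment group comparisons". Section 11.6.3.1 describes the additional AE analyses as descriptive.

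**SAP general rule.** SAP 6.1 states that Blaker confidence intervals for binomial proportions and "differences in binomial proportions will be computed for safety variables".

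**SAP safety sections.** On solicited events, 9.3.1 says "The number and percent of subjects reporting at least one treatment-emergent solicited adverse event will be summarized for each solicited adverse event", with a Blaker interval. On all-cause unsolicited AEs, 9.3.2 says "The proportion of subjects reporting at least one unsolicited adverse event will be summarized by MedDRA system organ class and preferred term", again with a Blaker interval. Neither passage specifies a difference for these events. A difference with an interval and a Fisher p-value is specified only for the primary safety endpoint (9.3.2 and 9.4, Table 125). Section 10 plans no other analyses.

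**The concern.** The one between-arm estimate depends on the investigator's judgement of relatedness. By its title, Table 125 also leaves out solicited events, even those judged related. Protocol 2.3.1.1 lists vaginal discharge as the most likely effect of the product, and abnormal vaginal discharge is a solicited event. The effects most expected of a vaginal powder therefore get no estimated difference from placebo.

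In a blinded, placebo-controlled trial, the all-cause difference is the safety estimate that does not rest on a causality call. The plan collects the data for it and displays the two arms separately, but does not say how large the difference is or how precisely it is known. SAP 6.1 suggests that it will.

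**Working it through.** **1. Objective, rule and shells side by side**

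| Events | SAP table | Shown by arm | Difference, ratio or test |
|---|---|---|---|
| Product-related unsolicited AEs | 125 | n, N, proportion, CI | Difference, CI, Fisher p |
| Each solicited event and the Any rows | 108 | n, %, Blaker CI | None |
| Solicited events by maximum severity | 110, 112 (109 and 111 pool the arms) | n, %, Blaker CI | None |
| Solicited events by week | 113–124 | n, % | None |
| All unsolicited AEs by SOC and PT | 126 | n, %, Blaker CI | None |
| Unsolicited AEs by severity and relationship | 128 (127 pools the arms) | n, %, event count | None |

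The rule in SAP 6.1 is carried out in one of these rows.

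**2. Group sizes**

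The documents give no power or precision figure for safety, so the group sizes come from the stated total of 228. Inputs (protocol 11.4): 30% against 15%, two-sided 5%, 70% power, 2:1 allocation, 10% dropout. With pooled rate (0.30 + 2×0.15)/3 = 0.20:

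n(placebo) = [1.96·√(0.20·0.80·1.5) + 0.524·√(0.30·0.70 + 0.15·0.85/2)]² / 0.15² = (0.960 + 0.274)² / 0.0225 ≈ 67.7, so 68.

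The total is 3 × 68 = 204, and 204/0.9 = 226.7, so 227. The stated 228 is the next multiple of three and splits into 152 and 76. I assume that all 228 receive a dose.

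**3. What separate intervals convey compared with a contrast**

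The protocol assumes no AE rates, so the true rates below are illustrative. Every pair of outcomes (153 × 77) was enumerated and weighted by its binomial probabilities. Two events were recorded: non-overlap of the two 95% Blaker intervals, and a two-sided Fisher p of at most 0.05.

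| True rates, LACTIN-V vs placebo | Intervals do not overlap | Fisher rejects |
|---|---|---|
| Equal (5% to 46%) | 0.3–0.5% | 3.3–4.5% |
| 15% vs 5% | 30–31% (depends on search grid) | 61% |
| 40% vs 20% | 62% | 87% |
| 46% vs 30% | 34% | 65% |

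The 46% is the vaginal discharge figure that protocol 2.3.1.1 reports for the 24 women of LV-006. It matches 11/24 = 45.8%, both arms together. The 30% is assumed.

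**4. A worked example of the missing column**

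Suppose Table 108 showed 70/152 (46%, Blaker 38–54%) and 23/76 (30%, Blaker 21–41%). The intervals overlap. The difference is 0.4605 − 0.3026 = 0.158. The Wilson limits are 0.383 to 0.540 and 0.211 to 0.413. The Newcombe interval is then:

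- lower: 0.158 − √[(0.4605 − 0.383)² + (0.413 − 0.3026)²] = 0.158 − 0.135 = 0.023
- upper: 0.158 + √[(0.540 − 0.4605)² + (0.3026 − 0.211)²] = 0.158 + 0.121 = 0.279

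The difference is 15.8 points (95% CI 2.3 to 27.9; Fisher p = 0.023). The shell as drafted would not show this.

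**The case against.** **Nothing mandatory was dropped.** This stands. A reader might infer that the SAP silently removed a required regression. The protocol's wording there is permissive, and the mandatory parts of 11.6.3 (event rates and proportions with exact intervals) are delivered by Tables 108–112 and 126. Leaving out an optional model does not need an entry in SAP Section 13.

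**The protocol itself defines the safety outcome.** This also stands. Product-related AEs and SAEs are the stated primary safety outcome, with one formal test. The general objective does not create a second endpoint that must be tested.

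**The overlap rule is not in the plan.** Correct. Nothing in the SAP tells readers to judge the arms by interval overlap, and the shells print counts and denominators from which anyone could compute a difference. A reader might conclude from the table of probabilities that the plan conceals real excesses. The documents do not support that: the information is there, and only the estimate and its interval are missing. The illustrative rates are no forecast either, since protocol 2.3.1.1 says AEs in LV-006 were evenly distributed between the groups.

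**SAP 6.1 already promises the differences, and the shells are only samples.** This is the strongest reply, but it does not close the gap. Sections 9.3.1 and 9.3.2 spell out what each table contains, and for these events they list no difference. A programmer working from them would produce none.

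**Conclusion.** The point holds as an internal inconsistency in the SAP and an incomplete answer to the trial's own safety objective. SAP 6.1 says difference intervals will be computed for safety variables. The detailed sections and shells do so only for product-related unsolicited AEs. Solicited events and all-cause AEs have no estimated difference, so the planned output contains no between-arm safety estimate that is independent of the relatedness judgement.

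The choice of primary safety outcome and its Fisher test are not at fault. The overlap calculation shows only how poorly two separate intervals serve as a comparison. At 152 and 76, across the unequal rates tried, non-overlap occurs in about 30–62% of trials and a direct test rejects in 61–87%. Those figures rest on assumed AE rates and full dosing of 228 women. The inconsistency itself rests on no assumption.

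**What to change.** - **Table 108:** add the LACTIN-V minus placebo difference with a 95% CI for each solicited event and for the Any rows. The shell lists 16 symptoms where 9.3.1 lists 17; frequent urination is missing and should be restored in the same edit.
- **Table 126:** add the same two columns to the Any SOC row and the SOC rows.
- **Table 125:** add a row for any AE regardless of relationship, and state whether it counts solicited as well as unsolicited events.
- **Interval method:** name it. SAP 6.1 specifies Blaker for safety differences, but the Blaker code in 6.1.1 covers single proportions only. The only difference code there is Newcombe's, listed under Wilson intervals. If Newcombe is used, amend 6.1 to say so, along with the difference interval in Table 125, whose footnote says Blaker.
- **Labelling:** present the additions as unadjusted estimates without p-values. With 17 solicited events, independent 5% tests would give a 1 − 0.95¹⁷ = 58% chance of at least one false signal. Keep the product-related Fisher test as the primary safety test.

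The cost is SAP wording, a few columns and one row. Data collection, alpha and sample size are unchanged. The downside is more unadjusted intervals to interpret.

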11.6.3.1 Analysis of Primary Safety Outcome Measure

The primary safety outcome measure is the proportion of participants reporting product-related AEs and SAEs in each study arm through Visit 7 (Week 24, Day 168).

The outcome will be assessed in the safety analysis population. The outcome will be reported by study arm. The point estimates for the arm-specific proportions and difference in proportions along with the corresponding standard errors will be reported. Fisher's exact test at the 5% two-sided level of significance level without adjustment for multiplicity will be used for the comparison of proportions between study arms.

As described in Section 11.6.3, additional descriptive analyses of adverse event data and clinical safety laboratory values will be performed.

11.6.3.2 Analysis of Secondary Safety Outcome Measure

The secondary safety outcome measure is the tolerability of LACTIN-V measured by the proportion of participants who discontinue study product due to adverse events in each study arm.

The outcome will be assessed in the safety analysis population. The outcome will be reported by study arm. The point estimates for the

arm-specific proportions and difference in proportions along with the corresponding standard errors will be reported. Fisher's exact test at the 5% two-sided level of significance level without adjustment for multiplicity will be used for the comparison of proportions between study arms.

11.6.4 Efficacy Analyses

11.6.4.1 Analysis of Primary Efficacy Outcome Measure

The primary efficacy outcome measure is the proportion of participants with a positive BV diagnosis in each study arm by Visit 4 (Week 12, Day 84) after study product administration.

As described in Section 3.1.2, the Amsel Criteria and Nugent criteria will be used to determine diagnosis of BV recurrence. Cumulative proportion of BV recurrence by Visit 4 is defined as follows: the numerator is the number of participants who experience recurrence at least once through Visit 4 in the particular analysis population and the denominator is the number of participants included in the particular analysis population.

The primary efficacy outcome measure will be assessed in the CC population. Use of the mITT population has previously been recommended by the FDA where missing values from participants who drop out early are imputed using Last Observation Carried Forward (LOCF) [25]. However, this includes participants who dropped out after completing at least one follow-up visit, but before their first positive diagnosis. LOCF would classify such participants as 'not recurrent.' Thus, it is possible that the estimated proportions of treatment successes in a study arm could be larger than they are in reality. Thus LOCF could result in an over-optimistic estimate of treatment effect, conflicting with the following rationale for using an ITT analysis population stated in ICH E9 [37]: "[ITT analysis] tends to avoid over-optimistic estimates of efficacy resulting from a per protocol analysis, since the non-compliers included in the [ITT] analysis set will generally diminish the estimated treatment effect." To assess the effect of the choice of analysis population on the primary analysis, the analysis will be repeated as a secondary analysis in the mITT and PP populations. The mITT population includes participants who discontinue for reasons other than lack of treatment effect, as well as participants with a missing or non-evaluable Amsel or Nugent result with no positive result at another visit. The missing results will be imputed using LOCF. To assess the effect of missing data and the method of imputation on the primary analysis, a sensitivity analysis will be performed. The details of the sensitivity analysis will be detailed in the Statistical Analysis Plan.

As described in Section 11.3, a test of hypothesis will be performed. The analysis will be based on comparisons of cumulative proportion of BV recurrence between study groups by the Visit 4 using the Pearson Chi-Square test (or, if more appropriate, Fisher's Exact Test) for differences in proportions between two independent groups. The point estimates for the within-arm proportions, odds ratio, and corresponding two-sided level 95% confidence interval will be reported. A secondary time-to-event analysis of the primary efficacy outcome measure will be performed. Details of the analysis will be included in the Statistical Analysis Plan.

